3.3 Discussion of Study Design

This prospective, non-controlled, international, multi-centre phase 3 study is designed to demonstrate that *Wilate* is efficacious in bleeding prophylaxis in patients with VWD.

Reduction of the annual bleeding rate (ABR) of patients with coagulation bleeding disorders such as haemophilia A has been used as an efficacy endpoint to reliably demonstrate the impact of prophylaxis on the bleeding rates of these patients.

In addition, it is expected that the quality of life of patients with VWD is considerably compromised. Therefore, it was considered valuable to investigate the QoL profile of enrolled patients, despite there not being any validated tools to determine QoL in patients with VWD.

4 STUDY POPULATION

4.1 Population Base

4.1.1 Number of Patients

Overall, around 40 PTPs aged ≥ 6 years at the time of screening will be enrolled into this study. Of the 40 patients, at least 5 patients should have type 3 VWD, at least 6 patients should be aged 6–11 years, and at least 6 patients should be aged 12–16 years.

4.1.2 Inclusion Criteria

Patients who meet all of the following criteria are eligible for the study:

1. Patients aged ≥ 6 years at the time of screening
2. VWD type 1 (baseline von Willebrand factor activity [VWF:RCO] < 30 IU/dL), 2A, 2B, 2M, or 3 according to medical history requiring substitution therapy with a VWF-containing product to control bleeding
3. Currently receiving on-demand treatment with a VWF-containing product **AND** having experienced at least 6 BEs (excluding menstrual bleeds) over a period of 6 months, with at least 2 of these BEs treated with a VWF-containing product **AND** having records available to reliably evaluate the type, frequency, and treatment of BEs in this 6-month period

OR

Having switched to prophylactic treatment with a VWF-containing product within the past 2 years **AND** having records available to reliably evaluate the type, frequency, and treatment of BEs over a period of 6 months of on-demand treatment

4. Female patients of child-bearing potential must have a negative urine pregnancy test at screening and agree to use adequate birth control measures; in case hormonal contraception is used, the medication class should remain unchanged for the duration of the study
5. Voluntarily given, fully informed written and signed consent obtained before any study-related procedures are conducted

4.1.3 Exclusion Criteria

Patients who meet any of the following criteria are *not* eligible for the study:

1. Having received on-demand or prophylactic treatment with a VWF-containing product but having *no* records available to reliably evaluate the type, frequency, and treatment of BEs over a period of at least 6 months of on-demand treatment
2. History, or current suspicion, of VWF or FVIII inhibitors
3. Medical history of a thromboembolic event within 1 year before enrolment
4. Severe liver or kidney diseases (alanine aminotransferase [ALAT] and aspartate transaminase [ASAT] levels >5 times of upper limit of normal, creatinine >120 $\mu\text{mol/L}$)
5. Platelet count $<100,000/\mu\text{L}$ at screening (except for VWD type 2B)
6. Body weight <20 kg at screening
7. Patients receiving, or scheduled to receive, immunosuppressant drugs (other than antiretroviral chemotherapy), such as prednisone (equivalent to >10 mg/day), or similar drugs
8. Pregnant or breast-feeding at the time of enrolment
9. Cervical or uterine conditions causing abnormal uterine bleeding (including infection, dysplasia)
10. Treatment with any IMP in another interventional clinical study currently or within 4 weeks before enrolment
11. Other coagulation disorders or bleeding disorders due to anatomical reasons
12. Known hypersensitivity to any of the components of the study drug

4.2 Prior and Concomitant Therapy

Patients receiving, or scheduled to receive, immunosuppressant drugs (other than antiretroviral chemotherapy), such as prednisone (equivalent to >10 mg/day), or similar drugs, and women having changed their hormonal contraception within 6 months before enrolment may not be enrolled.

Concomitant therapies not interfering with the objectives of the study are permitted. Details of any concomitant medications must be recorded in the electronic Case Report Form (eCRF).

Forbidden Medication

No VWF/FVIII concentrates other than Wilate must be administered (except for emergency situations).

Patients permanently switching to another product within the study participation period will be assessed as treatment failures in the efficacy analyses. However, there are exceptions to this rule. Patients will hence not be considered treatment failures in the efficacy analyses, if:

- the use of another VWF/FVIII concentrate was due to an emergency case (example: accident requiring treatment with VWF without patient or treating facility having access to Investigational Medicinal Product [IMP])
- the IMP was not available for the patient in time (example: patient experiences a severe bleed but does not have enough product available).

The reason for a patient switching to another VWF product should be clearly documented in the CRF (and patient diary, if appropriate).

4.3 Withdrawal and Replacement of Patients

4.3.1 Premature Patient Withdrawal

Patients have the right to withdraw from the study at any time for any reason, without the need to justify their decision. The investigator also has the right to withdraw patients in case of AEs, poor compliance, or other reasons.

For any withdrawals after study entry, the investigator will obtain all the required details and document the reason(s) for discontinuation. If the reason for withdrawal of a patient is an AE, the main specific event or laboratory test will be recorded, and the investigator will make thorough efforts to clearly document the outcome.

4.3.2 Patient Replacement Policy

Drop-outs will not be replaced.

4.3.3 Assignment of Patients to Treatment

The investigator will enter a unique identifier for each patient (consisting of the study code, centre code, and patient number) in both the eCRF and the confidential patient identification list and inform the monitor of any new patient enrolled.

Patients who enrol in the study will not be permitted to re-enrol.

4.4 Relevant Protocol Deviations

In case of any major protocol deviation, the investigator and Octapharma will decide on the further participation of the patient in this study after having discussed all relevant aspects.

5 INVESTIGATIONAL MEDICINAL PRODUCT

5.1 Characterisation of *Wilate*

Wilate, produced from the plasma of human donors, is presented as a powder and solvent for intravenous injection containing nominally 500 IU or 1000 IU human VWF and human FVIII per vial. The ratio between VWF ristocetin co-factor activity (VWF:RCo) and FVIII:C is 1:1.

The product contains approximately 100 IU/ml human VWF when reconstituted with 5 mL/10 mL water for injections with 0.1% polysorbate 80. The specific activity of *Wilate* is ≥67 IU VWF:RCo/mg protein.

The injection or infusion rate should not exceed 2–3 mL per minute.

5.2 Packaging and Labelling

Final labelling will comply with the national requirements of each country where the study is conducted.

5.3 Conditions for Storage and Use

The powder and solvent vials must be stored in a refrigerator at +2°C to +8°C (36°F to 46°F). The vials must be kept in the outer carton to protect from light and must not be frozen.

The product can be stored at room temperature (max. of +25°C or 77°F) for 2 months. In this case, the shelf-life expires 2 months after the product has been taken out of the refrigerator for the first time.

The investigator and any authorised personnel at the site will ensure that the IMP is stored in appropriate conditions with restricted access and in compliance with national regulations.

5.4 Dose and Dosing Schedule

5.4.1 *Wilate* Dosage for PK Assessment in Paediatric Patients

For the PK assessment in paediatric patients (6–16 years), a single dose of 60 ± 10 IU/kg will be administered.

5.4.2 *Wilate* Dosage for Prophylactic Treatment

For prophylactic treatment, *Wilate* should be administered 2–3 times per week at a dose of 20–40 IU/kg BW for 12 months.

The prophylactic dose for each patient will be determined by the Principal Investigator based on each patient's clinical condition and at the following time points:

- At the Baseline IVR Visit (see Section 6.1.2) in adult patients (≥ 17 years)
In adult patients, the first prophylactic dose will be administered at the time of the baseline IVR assessment.
- At the Baseline PK Visit (see Section 6.1.4) in paediatric patients (6–16 years)
In paediatric patients, the first prophylactic dose will be administered after completion of the PK phase.

In case of unacceptably frequent spontaneous breakthrough BEs (i.e., more than 2 spontaneous BEs or 1 major spontaneous BE within a 30-day period), the dose of *Wilate* should be increased by approximately 5 IU/kg (depending on the entire content of the additional vials that need to be reconstituted). If, after a dose increase, patients still experience more than 2 spontaneous bleeding episodes, the dosing interval should be shortened from 2 times per week to 3 times per week.

5.4.3 *Wilate* Dose for the Treatment of Breakthrough BEs

The dose (and duration) of treatment of BEs will depend on the location and extent of bleeding and on the clinical condition of the patient.

Generally, 1 IU/kg BW VWF:Ac (VWF:RCo) and FVIII:C raises the plasma level by 1.5–2% of normal activity for the respective protein. Usually, about 20–50 IU *Wilate*/kg BW are necessary to achieve adequate haemostasis. This will raise the VWF:Ac (VWF:RCo) and

FVIII:C in the patients by approx. 30–100%.

The following should be used to guide dosing in the treatment of BEs:

Dose type	Minor haemorrhage*	Major haemorrhage
Loading dose	20–40 IU/kg	40–60 IU/kg
Maintenance dose	20–30 IU/kg every 12–24 hours	20–40 IU/kg every 12–24 hours
Therapeutic goal	Maintain VWF:Ac (VWF:RCo) and FVIII:C trough levels >30%	Maintain VWF:Ac (VWF:RCo) and FVIII:C trough levels >50%

*Menstrual bleeds of regular intensity (i.e., minor menstrual haemorrhage) will be considered normal and are not expected to require therapy unless deemed necessary by the investigator and/or the patient.

5.4.4 Surgical Prophylaxis

For prevention of bleeding in case of surgery, levels of VWF:Ac (VWF:RCo) ≥ 60 IU/dL ($\geq 60\%$) and FVIII:C levels ≥ 40 IU/dL ($\geq 40\%$) should be achieved.

An appropriate dose should be re-administered every 12–24 hours of treatment. The dose and duration of the treatment depend on the clinical status of the patient, the type and severity of bleeding, and VWF:Ac (VWF:RCo) and FVIII:C levels.

In patients receiving FVIII-containing VWF products, plasma levels of FVIII:C should be monitored to reveal sustained excessive FVIII:C plasma levels, which may increase the risk of thrombotic events.

The following should be used to guide dosing in surgical prophylaxis:

Dose type	Minor surgeries (incl. tooth extractions)	Major surgeries
Loading dose	30–60 IU/kg	40–60 IU/kg
Maintenance dose	15–30 IU/kg, or half the loading dose, every 12–24 hours for up to 3 days	20–40 IU/kg, or half the loading dose, every 12–24 hours for up to 6 days or longer
Therapeutic goal	Achieve VWF:Ac (VWF:RCo) peak levels of 50% after loading dose and trough levels of >30% during maintenance doses	Achieve VWF:Ac (VWF:RCo) peak level of 100% after loading dose and trough levels of >50% during maintenance doses

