Good	Bleeding was completely stopped, but time and/or dose slightly exceeded expectations
Moderate	Bleeding could be stopped only by significantly exceeding time and/or dose expectations
None	Bleeding could be stopped only by using other VWF-containing products
The proportion of BEs successfully treated with IMP will be evaluated for all BEs taken together and by BE severity. All efficacy ratings assessed as either 'excellent' or 'good' will be considered 'successfully treated.'	
Surgical Prophylaxis Data	
The following surgery-related parameters will be documented:	

▪ Type of surgery (planned or emergency)▪ Location of surgery▪ Severity of surgery (minor, major)▪ Expected and actual duration of surgery▪ Expected average/maximum and actual blood loss▪ Pre-, intra-, and postoperative IMP administration data▪ Pre-, intra-, and postoperative FVIII and VWF:Ac plasma levels▪ Routine safety laboratory▪ Presence of wound haematomas▪ Vital signs▪ Details on concomitantly administered medications▪ Blood transfusion requirements▪ Brief narrative describing the outcome of the intervention▪ Efficacy assessment at the end of surgery by surgeon▪ Efficacy assessment at the end of the postoperative period by haematologist▪ Overall efficacy assessment at the end of the postoperative period by the investigator▪ Monitoring of AEs	

Name of Sponsor/Company: Octapharma AG	
Name of Investigational Product: Wilate	Protocol Identification Code: WIL-31
Name of Active Ingredient: Factor VIII/VWF concentrate human	Date of Final Protocol: 01-Mar-2021

Surgeries are defined as major if any of the following criteria are met:

- General or spinal anaesthesia required
- Opening into the great body cavities required
- Severe haemorrhage during surgery possible
- Haemostatic therapy for at least 6 days required
- Orthopaedic interventions involving joints (ankle, knee, hip, wrist, elbow, shoulder)
- 3rd molar extraction or extraction of ≥ 3 teeth
- Surgeries/conditions in which the patient's life is at stake

The classification is made prospectively. All other surgeries are classified as **minor**.

Efficacy in Surgical Prophylaxis

Efficacy will be assessed at the end of surgery by the surgeon and at end of the postoperative period by the haematologist. In both cases, predefined assessment criteria will be used. In addition, an overall assessment of efficacy will be made at the end of the postoperative period by the investigator.

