7.2.4 Surgical Prophylaxis Data

The following surgery-related parameters will be documented:

- Type of surgery (planned or emergency)
- Location of surgery
- Severity of surgery (minor, major) (see definitions under **(a)** below)
- Expected and actual duration of surgery
- Expected average/maximum and actual blood loss
- Pre-, intra-, and postoperative IMP administration data (see definitions under **(b)** below)
- Pre-, intra-, and postoperative FVIII and VWF:Ac plasma levels (see definitions under **(b)** below)
- Routine safety laboratory
- Presence of wound haematomas
- Vital signs
- Details on concomitantly administered products
- Blood transfusion requirements
- Brief narrative describing the outcome of the intervention
- Efficacy assessment at the end of surgery by surgeon (see **Section 7.2.5.1**)
- Efficacy assessment at the end of the postoperative period by haematologist (see **Section 7.2.5.2**)
- Overall efficacy assessment at the end of the postoperative period by the investigator (see **Section 7.2.5.3**)
- Monitoring of AEs

For details regarding the time points of data collection, refer to the flow chart of assessments for surgical prophylaxis on **page 27**.

(a) Severity of surgery

Surgeries are defined as **major** if any of the following criteria are met:

- General or spinal anaesthesia required
- Opening into the great body cavities required
- Severe haemorrhage during surgery possible
- Haemostatic therapy for at least 6 days required
- Orthopaedic interventions involving joints (ankle, knee, hip, wrist, elbow, shoulder)
- 3rd molar extraction or extraction of ≥ 3 teeth
- Surgeries/conditions in which the patient's life is at stake

The classification is made prospectively. All other surgeries are classified as **minor**.

(b) Definitions of periods and time points before, during, and after surgery

- **Preoperative** is defined as the time period of up to 3 hours before the start of surgery.
- The **end of surgery** is defined as the time immediately after the last surgical suture.
- **Postoperative** is the period from the end of surgery to the time the patient returns to his or her regular VWF treatment regimen.
- The **end of the postoperative period** is the time the patient returns to his or her regular VWF treatment regimen.

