At the end of each BE treated with Wilate, treatment efficacy will be assessed by the patient (together with the investigator in case of on-site treatment). The efficacy assessment of treatment of BEs includes the categories 'excellent', 'good', 'moderate' and 'none'. All efficacy ratings assessed as either 'excellent' or 'good' will be considered 'successfully treated.'

Efficacy in the surgical prophylaxis

Efficacy in surgical prophylaxis will be analyzed descriptively, presenting summary tables and listing on all aspects of surgical treatment and procedures as well as efficacy ratings.

The following surgery-related parameters will be presented:

- Location, severity (minor or major, for definitions see protocol), and type (planned or emergency) of surgery
- Expected and actual duration of surgical procedure
- Expected average/maximum and actual blood loss
- Pre-, intra-, and/or postoperative IMP administration data (only listed)
- Pre-, intra-, and postoperative FVIII:C and VWF:Ac plasma levels (dependent on the availability of data)
- Routine safety laboratory
- Details on concomitantly administered products, except standard anesthetic products (only listed)
- Blood transfusion requirements (only listed)
- Brief narrative describing the outcome of the intervention (only listed)
- Assessment of efficacy of surgical prophylaxis:
 1. at the end of surgery by the surgeon
 2. at end of the postoperative period by the hematologist
 3. overall efficacy assessment taking both the intra- and postoperative assessments into account, assessed by the Investigator.
- Number of successfully treated surgeries ('excellent' or 'good' overall efficacy rating)

Procedures that meet the following criteria are considered as 'major' surgeries. All other procedures are considered 'minor'

- General or spinal anaesthesia required
- Opening into the great body cavities required
- Severe haemorrhage during surgery possible
- Haemostatic therapy for at least 6 days required
- Orthopaedic interventions involving joints (ankle, knee, hip, wrist, elbow, shoulder)
- 3rd molar extraction or extraction of ≥ 3 teeth
- Surgeries/conditions in which the patient's life is at stake

Time periods relative to surgical procedures are defined as:

Statistical Analysis Plan	Version 6.0		Page 17 of 24
Sponsor	Octapharma	Protocol No	WIL-31

- Preoperative is defined as the time period of up to 3 hours before the start of surgery.

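### For third-molar extractions and extractions of 3 or more teeth, the surgical dosing table (minor) and the severity definition (major) contradict each other

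*Protocol*

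**What the plan says.** **Dosing.** Protocol 5.4.4 guides surgical dosing with a two-column table, one column for minor and one for major surgery. The minor column is headed "Minor surgeries (incl. tooth extractions", closing the bracket with no limit on tooth type or number. The study outline carries the same table and heading.

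- Minor maintenance: "15–30 IU/kg, or half the loading dose, every 12–24 hours for up to 3 days". Minor goal: "Achieve VWF:Ac (VWF:RCo) peak levels of 50% after loading dose and trough levels of >30% during maintenance doses".
- Major maintenance: "20–40 IU/kg, or half the loading dose, every 12–24 hours for up to 6 days or longer". Major goal: a VWF:Ac peak of 100% and troughs above 50%.

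**Classification.** The study outline, under the surgical prophylaxis data, says "Surgeries are defined as major if any of the following criteria are met", so one criterion is enough. Protocol 7.2.4 has the same rule and list. One entry is "3rd molar extraction or extraction of ≥ 3 teeth". Every surgery that meets no criterion is minor, and "The classification is made prospectively".

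**SAP.** Section 4.7.3 repeats the list: "Procedures that meet the following criteria are considered as 'major' surgeries. All other procedures are considered 'minor". It refers to the protocol for the definitions of severity. The SAP has no surgical dosing table.

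**The concern.** A site planning a third-molar extraction has two places to look. The dosing table names tooth extractions and puts them in the minor column. The severity definition names this extraction and makes it major. Section 5.4.4 does not refer to 7.2.4, and nothing says how the bracketed words in the heading relate to the definition.

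What is at stake is mainly the factor cover. Two sites that both follow the protocol could aim at different plasma levels, and plan different lengths of cover, for the same operation. The second and lesser issue is interpretation: a case can be recorded as major although the site worked to the goals of the minor column.

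**Working it through.** No statistical figure is stated on this point, so the check sets the texts side by side.

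**Step 1. Which extractions are affected?**

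| Extraction | By the heading in 5.4.4 and the outline | By 7.2.4, the outline list and SAP 4.7.3 |
|---|---|---|
| 1–2 teeth, none a third molar | Minor | Minor, unless another major criterion applies (for example general anaesthesia) |
| Any third molar | Minor | Major |
| 3 or more teeth | Minor | Major |

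The tooth criterion conflicts with the heading in the last two rows only.

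**Step 2. How far do the columns of the 5.4.4 table differ?**

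| Item | Minor column | Major column | Overlap |
|---|---|---|---|
| Loading dose (IU/kg) | 30–60 | 40–60 | 40–60 |
| Maintenance dose (IU/kg) | 15–30 | 20–40 | 20–30 |
| Maintenance interval | 12–24 hours | 12–24 hours | Identical |
| Maintenance duration | Up to 3 days | Up to 6 days or longer | Both allow short courses; the upper limits differ |
| VWF:Ac peak goal | 50% | 100% | None as stated; ratio 100/50 = 2 |
| VWF:Ac trough goal | >30% | >50% | A trough above 50% meets both; the minimum differs |

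Many actual doses fit both columns; a loading dose of 50 IU/kg is one. The clear differences are therefore the plasma-level goals and the duration.

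**Step 3. Does it reach the planned analyses?**

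- *Severity tables.* SAP 4.7.3 uses the list in 7.2.4 and no other, so the class assigned to an extraction is not in doubt there.
- *Surgical efficacy.* It is an exploratory endpoint (Protocol 3.1.3, SAP 4.7.3) and is analysed descriptively. Protocol 9.2.2 gives the distribution of ratings over all procedures, and SAP 4.7.3 counts successfully treated surgeries. Neither specifies efficacy by minor or major class.
- *Ratings.* The surgeon's rating compares blood loss with expectation (Protocol 7.2.5.1). The haematologist's rating rests on postoperative bleeding and how it was controlled (7.2.5.2). Neither uses the plasma-level goals.
- *Consumption.* The secondary endpoint covers prophylaxis, not surgery (Protocol 3.1.2, SAP 4.7.2).
- *TABR.* SAP 6.1 removes the surgery period, which runs to the actual last dose given for surgery or for prophylaxis after it. As an illustration, take the difference between the two stated limits: 6 − 3 = 3 days, and 3 / 365.25 = 0.0082, about 0.8% of a patient-year. The major limit is open-ended, so this is not an upper bound. Because actual dates are used, the table enters only through what sites did.

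**The case against.** **The terms are defined elsewhere in the protocol.** The columns are for minor and major surgeries, the protocol defines those terms through one list, and the class is set before the operation. A site can read the bracketed words as meaning only those extractions that 7.2.4 leaves minor. That reading is reasonable, but neither the heading nor 5.4.4 states it, and 5.4.4 does not point to the definition. It lowers the chance of error without removing the contradiction.

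**The table is guidance.** Section 5.4.4 makes dose and duration depend on clinical status, bleeding and measured levels, and the dose ranges overlap. This stands, and it is why the doses themselves are not counted as a clear conflict. The section also opens with a general surgical level of VWF:Ac of at least 60 IU/dL, so the 50% peak in the minor column is not a clean comparator. That level does not settle which column applies.

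**A stronger reading is tempting.** A reader might infer that factor cover, consumption and efficacy ratings will be reported under a class whose goals were not aimed for, and so be distorted. The documents do not support this. They specify no efficacy or factor-cover output by severity class, and the ratings do not use the plasma goals. The postoperative criteria do ask whether extra dosing had been anticipated for the type of procedure, but they do not tie that expectation to a column of the table.

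**Conclusion.** The contradiction is real and literal, and confined to third-molar extractions and extractions of 3 or more teeth. For these, the protocol gives two VWF:Ac peak goals (50% and 100%), two trough goals (above 30% and above 50%) and two upper limits for maintenance (3 days, and 6 days or longer). It should be resolved because it bears on cover at surgery, and the correction is specific and small.

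For the analysis the effect is small. It would be wrong to conclude that all tooth extractions are affected, that the SAP contradicts itself, or that the primary result is at risk.

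This rests on reading the heading as it stands, without an unstated limit. The documents do not say how many such extractions took place; if there were none, only the wording is affected. No view is taken on which column is clinically right.

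**What to change.** Reconcile the minor-column heading in Protocol 5.4.4 and in the study outline with the severity definition in Protocol 7.2.4, its outline copy and SAP 4.7.3, so that each extraction falls in one column only. The clinical team decides which. A reference from 5.4.4 to 7.2.4 would make the link explicit.

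The cost is one heading in two places, plus the amendment handling that Protocol 10.4 requires. If the team changes the definition instead, the list in SAP 4.7.3 must follow.

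No SAP listing of the dosing column used is needed. That item is not among the data to be recorded, and with overlapping ranges it often could not be derived. SAP 6.0 is dated 23 September 2022, after the planned clinical end in Q1 2022, so some of these extractions may already have been done. For those, SAP 4.7.3 already presents severity, lists the actual IMP administration and gives plasma levels where available, which shows the cover given.
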